### Follow-up adjusted incidence rate.

Follow-up adjusted incidence rate will be summarized by system organ class and preferred term by study group. Follow-up adjusted incidence rate – defined as the number of subjects who experienced an event divided by the total of entire follow-up time among the subjects in the analysis population. The entire follow-up time for subject is defined as the time from the first dose until the end of study day. Each subject will be counted only once within each category. A similar table will also be based on total number of events divided by the total of entire follow-up time among the subjects in the analysis population. This may count a subject more than once within each category of they experienced an event more than once.

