## 3.6.2. External data

For CS3B, the efficacy set at Day 183 and Day 302 as defined for the final analysis of CS3B will be utilized.

The following table describes analysis sets for the historical data and how they will be referenced in the remainder of the document.

Table	1:	Analy	sis	set
-------	----	-------	-----	-----

Analysis Set Label	Description
CS3B Day 183 efficacy set	This is the 'Evaluable set for Day 183' referenced in the Final CS3B CSR. It consists of N=37 sham control and N=73 12 mg nusinersen participants.
CS3B Day 302 efficacy set	This is the 'Evaluable set for Day 302' referenced in the Final CS3B CSR. It consists of N=28 sham control and N=49, 12 mg nusinersen participants.
Matched Sham Set	Analysis set for main comparisons of higher dose versus sham control.
	Subset of the 37 sham control participants in the CS3B Day 183 efficacy set similar to higher dose 232SM203 participants and all higher dose participants in the ITT set.
Matched Sham Set (sensitivity)	Subset of the 37 sham control participants in the CS3B Day 183 efficacy set similar to all N=75 232SM203 participants in the ITT set.
Greedy matched set (sensitivity)	Set of CS3B sham and 232SM203 higher dose participants matched by greedy matching. Note that not all higher dose participants will have a match.

Page 20

Product: Nusinersen	Statistical Analysis Plan
Study: 232SM203	Version: 3.0 Final

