## Sensitivity analyses

- o Repeated using CS3B sham Day 183 matched to 232SM203 efficacy set (sensitivity)
- Repeated using Greedy matched set (sensitivity)
- Adjustment of ranking criteria for JRT for withdrawals not due to death In order to test the sensitivity of handling withdrawals not due to death, ranking criteria will be adjusted as a sensitivity analysis for JRT These analyses will be performed as described in Section 6.1
- Adjustment of ranking criteria for JRT for permanent ventilation
- Main analysis will be repeated using an ANCOVA model where the variance in each treatment group is estimated separately

In order to examine the impact of considering permanent ventilation in evaluation of this endpoint the ranking criteria will be adjusted as sensitivity analysis for JRT. These analyses will be performed as described in Section 6.1.

• Exclusion of deaths from MI model

The MI model will be run for CHOP INTEND total score for the ITT population excluding data from any subjects who died prior to Day 183, so that missing data for survivors are not influenced by any systematic difference there may be in data from subjects who died. The joint rank analysis will then be conducted using these imputed datasets for survivors and deaths will be ranked the lowest based on time of death. The pvalue from the joint rank analysis with MI will be presented as per the main analysis.

• Data truncated to include only up to and including Day 183

Product: Nusinersen	Statistical Analysis Plan
Study: 232SM203	Version: 3.0 Final

In the event that a participant has CHOP INTEND missing items at Day 183 then data from later visits is utilized as part of interpolation. Some of the subjects in the CS3B study only have data up to Day 183 before the study was stopped in contrast to 232SM203 where all subjects potentially could be followed to Day 302. In order to investigate the sensitivity of the analysis to this truncation an additional analysis will be performed where only the data up to and including Day 183 is utilized from both CS3B and 232SM203 and the item level imputation approach described in Section 6.1 is applied.

- The main analysis will be repeated incorporating Jump to reference in the MI step.
- The main analysis will be repeated for the following subgroups:
  - disease duration
  - baseline CHOP INTEND

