### 7. Safety Endpoints

### 7.1.1. Adverse events

The analysis of safety will be performed using the respective Safety Sets and presenting by 232SM203 treatment groups. The sham participants from safety sets from CS3B will be included for the analysis of adverse events.

All AEs will be analyzed based on the principle of treatment emergence where treatment emergence will be relative to the first dose of nusinersen. An AE will be regarded as treatmentemergent if it was present prior to receiving the first dose of nusinersen and subsequently worsened in severity or was not present prior to receiving the first dose of nusinersen but subsequently appear. Refer to Appendix A for more details about AE with missing start or stop dates.

A participant having the same AE preferred term more than once will be counted only once in the incidence for that event. Multiple occurrences of the same adverse event for the same subject will all be counted in the frequency for that adverse event.

Product: Nusinersen	Statistical Analysis Plan
Study: 232SM203	Version: 3.0 Final

The occurrence of the AE with the greatest severity will be used in the calculation of incidence by severity. The AE relationship to treatment or LP/sham procedure is captured as related or not related. In the event the relationship is missing then this will be considered related.

Due to the long half-life of nusinersen, analyses of treatment-emergent adverse events will include all events reported during the study. Adverse Events will be coded using the Medical Dictionary for Regulatory Activities.

The following presentations will be shown:

an overall summary showing, for each treatment group, the number and percentage of subjects with an adverse event, a mild, moderate or severe event, an event related to study drug, an event related to lumbar puncture /sham procedure, a serious event, a serious event related to study drug, an event leading to study drug withdrawal, an event leading to study withdrawal, and a fatal event.

incidence and frequency by system organ class and preferred term

incidence and frequency by preferred term

incidence and frequency, by preferred term, in at least 5% of subjects in any treatment group

incidence of adverse events by maximum severity by preferred term

incidence and frequency of severe events by system organ class and preferred term

incidence and frequency of events related to study drug by system organ class and preferred term

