#### Follow-up adjusted incidence rate

Follow-up adjusted incidence rate will be summarized by system organ class and preferred term by study group. Follow-up adjusted incidence rate, defined as the number of subjects who experienced an event divided by the total of entire follow-up time among the subjects in the analysis population. The entire follow-up time for subject is defined as the time from the first dose until the end of study day. Each subject will be counted only once within each category. A similar table will also be based on total number of events divided by the total of entire follow-up time among the subjects in the analysis population. This may count a subject more than once within each category if they experienced an event more than once.

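### The subject-based follow-up adjusted incidence rate keeps person-time after the first event, so for common adverse events it still depends on length of follow-up

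*SAP*

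**What the plan says.** The Part B infantile-onset SAP, under the heading on the follow-up adjusted incidence rate in section 7.1.1, gives a measure by system organ class (SOC) and preferred term that is "defined as the number of subjects who experienced an event divided by the total of entire follow-up time". It adds: "Each subject will be counted only once within each category." The denominator is also fixed: "The entire follow-up time for subject is defined as the time from the first dose until the end of study day." The later-onset SAP repeats the definition in section 6: "defined as the number of subjects who experienced an event divided by the total of entire follow-up time among the subjects in the analysis population". Since entire follow-up is defined explicitly, the text cannot be read as stopping time at the first event.

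Both SAPs plan a second table in the same paragraph: "A similar table will also be based on total number of events divided by the total of entire follow-up time".

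On the groups shown, infantile section 7.1.1 states: "The sham participants from safety sets from CS3B will be included for the analysis of adverse events." Infantile section 3.2 places matched CS3B sham beside 50/28 mg for key adverse event displays. Later-onset sections 3.2 and 6 plan adverse event presentations of matched CS4 sham against the higher dose.

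**The concern.** A measure named as adjusted for follow-up should not move with follow-up when the underlying risk is the same. This one does. After a first event the subject is out of the numerator for good but goes on adding time to the denominator, so the value falls as follow-up lengthens. For very common events it tends to one over the mean follow-up and hardly reflects the hazard at all.

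The document itself points to unequal follow-up against sham. CS3B was stopped early (infantile section 2.4), and in the sensitivity analyses of section 6.3.1: "Some of the subjects in the CS3B study only have data up to Day 183 before the study was stopped", while 232SM203 participants could be followed to Day 302. The sample size assumes a 23% survival benefit over sham (section 2.3), so deaths would shorten sham follow-up further. CS4 had a planned follow-up of 15 months (later-onset section 2.4.1), longer than Part B.

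The direction matters. Shorter CS3B follow-up would raise the sham value and flatter 50/28 mg. Longer CS4 follow-up would do the opposite. A reader who takes the name at face value would compare columns that are not comparable for common events.

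**Working it through.** The SAPs give no figure for this measure, so there is nothing to reproduce. The check asks what the defined quantity returns when two groups have the same constant hazard λ.

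**Inputs**
- 232SM203 follow-up from first dose: total duration of 323 to 420 days less 21 days of screening (infantile section 3.3, later-onset section 3.2) gives 302 to 399 days.
- CS3B sham: the Day 183 efficacy set in infantile section 3.6.2 is described as "It consists of N=37 sham control and N=73 12 mg nusinersen participants"; the Day 302 set has 28 sham. The difference is 37 − 28 = 9. *Assumption:* 9 sham followed to Day 183 and 28 to Day 302, a mean of 273 days. This ignores deaths.
- *Assumption:* mean sham follow-up of 200 days, as a more severe case. No document gives this figure.
- CS4: 15 planned months, taken as 456 days. CS4 also stopped early, so actual follow-up may be shorter.
- Event frequencies are assumed and shown as a range.

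**Formulas**
- SAP quantity for one follow-up length T: (1 − exp(−λT)) / T.
- SAP quantity for mixed follow-up: Σ(1 − exp(−λTᵢ)) / ΣTᵢ.
- Ratio: shorter-follow-up group over longer-follow-up group. Equal hazards should give 1.00.

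**Event with 70% incidence at Day 302**

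λ = −ln(0.30)/302 = 0.003987 per day. Values per day:
- 302 days: 0.70/302 = 0.0023179
- 9 to Day 183 and 28 to Day 302: (9 × 0.5179 + 28 × 0.70) / (9 × 183 + 28 × 302) = 24.261/10,103 = 0.0024014
- 200 days: 0.5495/200 = 0.0027474
- 399 days: 0.7962/399 = 0.0019955
- 456 days: 0.8376/456 = 0.0018369

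Ratios:
- Infantile, sham mix v 302: 0.0024014/0.0023179 = 1.04
- Infantile, 200 v 302: 0.0027474/0.0023179 = 1.19
- Later-onset, 399 v 456: 0.0019955/0.0018369 = 1.09
- Later-onset, 302 v 456: 0.0023179/0.0018369 = 1.26

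**Other frequencies, same formula**

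| Incidence at Day 302 | Infantile: sham mix v 302 | Infantile: 200 v 302 | Later-onset: 399 v 456 | Later-onset: 302 v 456 |
|---|---|---|---|---|
| 10% | 1.003 | 1.02 | 1.01 | 1.03 |
| 40% | 1.02 | 1.08 | 1.04 | 1.12 |
| 70% | 1.04 | 1.19 | 1.09 | 1.26 |
| 90% | 1.06 | 1.31 | 1.12 | 1.40 |

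In the infantile columns the higher value falls on sham; in the later-onset columns it falls on 50/28 mg.

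**After the change**

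If time stops at the first event, the expected time at risk per subject is (1 − exp(−λT))/λ. Dividing the expected number of first events by this returns λ for any T, so the ratio is 1.00. A simulation of 400,000 subjects per group at 183 and 302 days and one event per person-year agrees: the SAP quantity is 0.786 v 0.680, first events over time at risk is 1.00 v 1.00, and all events over total follow-up is also 1.00 v 1.00.

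**The case against.** The strongest reply is that each SAP already plans an adequate measure beside this one. The events-over-total-follow-up table is not distorted by length of follow-up under a constant rate, and plain incidence, adverse events over time, and events within 24 and 72 hours of dosing or sham are also shown. That stands, and it limits the harm. It does not repair the subject-based table, which answers a different question: an event-count rate can be driven by a few subjects with many events.

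A reader might infer more than the documents support:
- *That the quantity is not a rate at all.* It has units of one over time and is openly defined. What it is not is an incidence rate on time at risk.
- *That it is the planned correction for unequal follow-up.* It is one of two tables.
- *That it differs whenever follow-up differs.* That follows for a constant hazard and one follow-up length per group; mixed follow-up distributions could coincide.
- *That the distortion is typically 1.2 to 1.4.* Those values need very common events with either an assumed 200 sham days or the shortest Part B follow-up set against the full planned CS4 duration. Follow-up closer to the documents gives 1.04 and 1.09 for a 70% event.
- *That sham columns are certain to appear.* Neither definition says so. The later-onset SAP makes the comparison of the two 232SM203 arms its main safety analysis; these share a visit schedule, so little distortion should arise there.

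The remedy also has a limit. If adverse events cluster around loading, a first-event rate varies with follow-up too. As an illustration, with a hazard four times higher up to Day 64 and a 70% event, it gives 1.16 for 200 v 302 days and 1.12 for 302 v 456 days.

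**Conclusion.** The point holds as an error of definition in a descriptive safety table, present in both Part B SAPs. The size is negligible to about 3% for events near 10% incidence. It grows for common preferred terms and SOC totals: for a 70% event, about 1.04 to 1.19 in the infantile comparison and 1.09 to 1.26 in the later-onset one, in opposite directions relative to 50/28 mg. These figures rest on equal constant hazards, assumed event frequencies and assumed follow-up. The later-onset upper value uses planned CS4 follow-up although CS4 stopped early; if actual CS4 follow-up was close to that of Part B, the distortion there largely disappears. The presence of sham columns is inferred. No formal test is affected, because safety lies outside the infantile testing sequence and the later-onset SAP plans no confirmatory safety test.

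**What to change.** In the infantile-onset SAP (section 7.1.1) and the later-onset SAP (section 6), define follow-up for the subject-based rate as the time from first dose, or first sham procedure for sham participants, to the first event in that SOC or preferred term, or to end of study if there is none. Keep the event-count table on entire follow-up. State which groups the two tables include, and note that comparing the rates across unequal follow-up assumes a roughly constant hazard. The cost is a sentence or two in each SAP and standard programming; no new data are needed.

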### Note on capture of severity and seriousness in CS3B.

In CS3B the eCRF captured detail for each investigator term for decreases in severity and changes from serious to non-serious. In 232SM203, the decrease in severity and change from serious to non-serious is not captured. In all studies worsening in severity and moving from non-serious to serious is captured.

In presenting CS3B as part of 232SM203 reporting, consistent with how these studies were originally reported in the following two scenarios:

1) where the severity decreases

2) where a serious event becomes non-serious

Only the first record will be considered treatment emergent so the actual reporting approach will be consistent with 232SM203.

Product: Nusinersen Study: 232SM203

### 7.1.2. Concomitant therapy and Procedure

A concomitant therapy is any drug or substance administered between screening and the final study visit/telephone call. Participants are instructed to contact their Investigators before taking any new medications, including nonprescription drugs and herbal preparations.

Throughout the study, Investigators or designated licensed physicians involved in the study may prescribe concomitant therapies (procedures) or treatments deemed necessary for AEs or to provide adequate supportive care.

Participants are prohibited from receiving other experimental or approved agents for the

treatment of SMA, including gene therapy, biological agent, or device, during the study. This includes marketed agents at experimental doses that are being tested for the treatment of SMA (oral albuterol/salbutamol, riluzole, carnitine, sodium phenylbutyrate, valproate, hydroxyurea, etc.).

All concomitant therapies will be coded using the World Health Organization drug

dictionary (WHO Drug). A concomitant procedure is any therapeutic intervention (e.g., surgery/biopsy, physical therapy) or diagnostic assessment (e.g., blood gas measurement, bacterial cultures) performed between Screening and the final study visit/telephone call. Concomitant procedures will be coded using MedDRA.

For the purposes of analysis, a concomitant therapy (including medication or procedure) is defined as any therapy that was taken or administered on or after the first injection of nusinersen (see appendix A). This includes therapies and procedures that were started prior to the initiation of injection of nusinersen if their use continued on or after the first injection of nusinersen. The number and percentage of subjects who were taking each type of concomitant therapy and procedures at baseline and during the study will be presented by preferred term.

The number and percentage of subjects who underwent each type of concomitant procedure during the study will be presented.

Concomitant therapies related to LP/Sham procedure will be summarized separately.

If there are a sufficient number of tests or treatments reported with indication of COVID-19, a separate summary of these will be provided.

Concomitant medications will also be reviewed by a medical reviewer prior to the lock to determine disallowed medications according to the protocol. These will be summarized separately.

Product: Nusinersen	Statistical Analysis Plan
Study: 232SM203	Version: 3.0 Final

### 7.1.3. Clinical laboratory data

Laboratory data will be evaluated to determine the incidence of abnormalities that emerge during the course of the study. Changes in laboratory evaluations will be presented relative to baseline, which is defined as the closest visit prior to the first dose.

The following clinical laboratory parameters are to be assessed:

Hematology panel: complete blood count with differential and platelet count (hematocrit, hemoglobin, platelets, red blood cell count [RBC], white blood cell count [WBC], basophils, eosinophils, lymphocytes, monocytes, neutrophils)

Blood chemistry panel: albumin, total bilirubin, direct and indirect bilirubin, alkaline phosphatase, alanine aminotransferase (ALT) (SGPT), aspartate aminotransferase (AST) (SGOT), gamma-glutamyl transferase (GGT), sodium, potassium, calcium, chloride, phosphate, blood urea nitrogen (BUN), creatinine, cystatin, creatine phosphokinase, creatine kinase, bicarbonate (CO2), glucose, total protein.

Urinalysis: specific gravity, pH, protein, glucose, ketones, bilirubin, blood, red blood cells, white blood cells, epithelial cells, bacteria, casts and crystals

Urine total protein assessed by local laboratories CSF analysis: RBC, WBC, protein, glucose.

Coagulation: PT (prothrombin time), aPTT (activated partial thromboplastin time), and INR (international normalized ratio).

Each hematology, blood chemistry, coagulation and CSF laboratory parameter will be flagged as "low", "normal" or "high" relative to the parameter's normal range or as "unknown" if no result is available.

For each urinalysis laboratory parameter, the number and percentage of subjects experiencing postdose shifts to abnormal will be summarized.

Summary statistics for actual values and change from baseline in laboratory values will be summarized by treatment group and visit. Box plots for chemistry, hematology and CSF showing mean value for each treatment group at each visit will also be presented.

Due to the impact of the COVID-19 pandemic on transport infrastructure, public health or humanitarian emergencies, certain sites may only be able to test blood and urine samples at a local laboratory instead of central one. The use of local labs which will use different techniques/equipment and reference ranges may introduce variability in the results.

To assess the variability of the results two summaries will be presented for actual and change from baseline by visit:

- summarize local laboratory and central laboratory results together
- summarize only central laboratory results

Listings of all chemistry, hematology, coagulation, CSF, urinalysis values and pregnancy test (serum and urine) will be provided.

For platelets a summary of the proportion of participants with a post baseline platelet count below the lower limit of normal on at least 2 consecutive measurements will be presented.

For study 232SM203, the urine protein positive (trace, +1, +2, +3, +4 or >0.2g/L) results will be presented, number of subjects with positive result at baseline, with a negative result at baseline and at least one and at least two positive post baseline result respectively. This display will not be presented for CS3B and CS4 since the total protein from local laboratories was not collected per protocol.

### 7.1.4. Neurological Examinations

### Hammersmith infant Neurological Examination (Sections 1 and 3) (HINE 1 and 3)

Sections 1 (neurological items) and 3 (behavior) of the HINE serve as the basis for neurological examinations. These are to be assessed at Screening, predose and at 3, 6, and 24 hours postdose on dosing days (Days 1, 15, 29, 64, 135, 183 and 279) and on Day 302/ET.

Product: Nusinersen	Statistical Analysis Plan
Study: 232SM203	Version: 3.0 Final

The neurological items comprise cranial nerve function (facial appearance, eye appearance, auditory response, visual response, sucking/swallowing), posture (head in sitting position, trunk in sitting position, arms at rest, hands, legs in sitting position, legs in supine and standing positions, feet in supine and standing positions), movements (quantity, quality), tone (scarf sign, passive shoulder elevation, pronation/supination, adductors, popliteal angle, ankle dorsiflexion, pulled to sit, ventral suspension), and reflexes and reactions (tendon reflexes, arm protection, vertical suspension, lateral tilting, forward parachute). Behavior is comprised of state of consciousness, emotional state, and social orientation. For each item, for each subject, the worst post-baseline and the best post-baseline outcomes will be determined and 'shift' tables showing the shifts from baseline to the worst and from baseline to the best post-baseline value will be presented. In this analysis, all assessments post the first dose at baseline will be considering post baseline visits. For any item where the investigators have entered scores outside the set of expected values the scores will be mapped prior to determining shifts as follows: for baseline values, to the next highest expected value and for post-baseline values to the next lowest expected value.

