## **Secondary Safety Objectives**

To examine the safety and tolerability of nusinersen administered intrathecally at higher doses to participants with SMA.

Secondary Safety Endpoints

- Incidence of AEs, including SAEs
- Shifts from baseline in clinical laboratory parameters, ECGs, and vital signs
- Change in growth parameters
- Shifts from baseline in coagulation parameters (aPTT, PT, and INR)
- Change in urine total protein
- Change from baseline in neurological examination outcomes
- The proportion of participants with a post baseline platelet count below the lower limit of normal on at least 2 consecutive measurements
- The proportion of participants with a post baseline QTcF of > 500 msec and an increase from baseline to any post baseline timepoint in QTcF of > 60 msec

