### **Reflex assessments**

### Acute effects after dosing: Reflex

On each dosing day, each predosing reflex will be compared with all the post dosing assessments with 24 hours to see if the subject has changed (gained or lost) or maintained, reflexes. For this comparison the pre-dose reflex status will be categorized into two categories: 0 and  $\geq 1$ . For each reflex, visit, pre-dose category the number and proportion of subjects who change or maintained will be presented.

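### Off-scale HINE Section 1 and 3 scores are mapped up at baseline and down afterwards, so an unchanged in-between score appears as a shift in the safety tables

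*SAP*

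**What the plan says.** The relevant text is in the Part B infantile-onset SAP, Section 7.1.4, under the heading for HINE Sections 1 and 3.

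- **Trigger.** "For any item where the investigators have entered scores outside the set of expected values the scores will be mapped prior to determining shifts".
- **Direction.** "for baseline values, to the next highest expected value and for post-baseline values to the next lowest expected value".
- **Output.** For each item, the "shifts from baseline to the worst and from baseline to the best post-baseline value will be presented".
- **What counts as post-baseline.** "all assessments post the first dose at baseline will be considering post baseline visits".
- **Schedule.** At screening; on each of the seven dosing days, once before the dose and three times after it (3, 6 and 24 hours); and once at Day 302 or early termination.

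The tables serve a listed secondary safety endpoint in Section 2.1: "Change from baseline in neurological examination outcomes". The later parts of Section 7.1.4 (acute reflex effects, acute effects on other assessments, chronic effects) neither change the mapping rule nor give a reason for it. The chronic-effects part also plans summaries of actual values and of change from baseline by arm and visit, with line plots of item means.

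**The concern.** A shift compares two values. If the same recorded score is moved up at one time and down at the other, the comparison contains a change that nobody observed. An infant whose item score sits between two expected values and stays there would be tabulated as having shifted.

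The shift tables are where a reader would look for neurological deterioration on the 50/28 mg regimen. False shifts occurring at a similar rate in both arms make a real difference between arms harder to see. The rule can also conceal a recorded gain. In the baseline-to-best table, whose purpose is to show the most favourable value reached, an infant who never changed could be shown as worse even at best.

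**Working it through.** The SAP gives no figure on this point, so there is nothing to reproduce. The check applies the rule directly.

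**Inputs.** The mapping directions come from Section 7.1.4. The expected score sets are not listed in the SAP, so {0,1,2,3}, {0,1,3} and {0,3} are assumed for illustration.

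**Formula.** For an off-scale score s lying between two expected values, let up(s) be the next expected value above it and down(s) the next one below. On-scale scores stay as they are. The tabulated shift under the plan is down(post) − up(baseline).

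**Unchanged score.** With post = baseline = s, the shift is down(s) − up(s). This is always negative, and its size is the gap between the two neighbouring expected values. Mapping in one direction gives down(s) − down(s) = 0 or up(s) − up(s) = 0.

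| Expected set | Recorded baseline → post | Recorded change | Plan's rule | Both down | Both up |
|---|---|---|---|---|---|
| {0,1,2,3} | 1.5 → 1.5 | 0 | 1 − 2 = −1 | 1 − 1 = 0 | 2 − 2 = 0 |
| {0,1,3} | 2 → 2 | 0 | 1 − 3 = −2 | 1 − 1 = 0 | 3 − 3 = 0 |
| {0,3} | 1 → 1 | 0 | 0 − 3 = −3 | 0 − 0 = 0 | 3 − 3 = 0 |
| {0,1,2,3} | 1.5 → 2.5 | +1 | 2 − 2 = 0 | 2 − 1 = +1 | 3 − 2 = +1 |
| {0,3} | 1 → 2 | +1 | 0 − 3 = −3 | 0 − 0 = 0 | 3 − 3 = 0 |
| {0,1,2,3} | 1.5 → 1 | −0.5 | 1 − 2 = −1 | 1 − 1 = 0 | 1 − 2 = −1 |
| {0,1,2,3} | 2 → 1.5 | −0.5 | 1 − 2 = −1 | 1 − 2 = −1 | 2 − 2 = 0 |
| {0,3} | 2 → 0 | −2 | 0 − 3 = −3 | 0 − 0 = 0 | 0 − 3 = −3 |

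The first three rows are the artefact. Rows four and five show recorded gains lost or reversed. The last three show what single-direction mapping can cost: a recorded fall that stays within one step disappears.

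**Which table is affected.** The schedule gives 7 × 3 postdose + 6 later predose + 1 at Day 302 = 28 post-baseline assessments per item. For the worst-value table, one repeat of the off-scale baseline score is enough to produce the false shift. For the best-value table, the off-scale score must persist throughout: one assessment at or above the mapped baseline value removes it.

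**Ends of the scale.** A baseline score above the maximum has no next highest value, and a post-baseline score below the minimum has no next lowest. The rule is undefined there.

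**The case against.** The strongest defence is that this is a deliberate worst-case convention. Mapped baseline is never below recorded baseline and mapped post-baseline is never above recorded post-baseline, so every recorded fall is still shown as a fall. Other safety rules in the same SAP lean the same way: an adverse event with missing relationship counts as related (Section 7.1.1), and one whose timing cannot be determined counts as on or after the first dose (Appendix A). That property is real and worth keeping somewhere. However, the SAP does not give this reason for the HINE rule. Nor does it explain why a best-value table should show worsening in an infant whose recorded score never moved.

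A second objection is that mapping everything down would hide real losses. That stands, as the fall from 2 to 0 on {0,3} shows. A change of direction must therefore come with a listing of raw scores.

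Three stronger readings are tempting and not supported.

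- **A rate of false worsening.** One might suppose that 5 to 10 percentage points are added per item. That merely restates an assumed 5 to 10% of off-scale stable scores. The SAP gives no frequency.
- **The endpoint rests on these tables alone.** It does not. The by-visit change summaries are also planned, and because the mapping is tied to determining shifts, they appear to be unmapped.
- **The direction is certain.** The SAP does not say that higher is better for HINE 1 and 3 items. The reflex analysis, which compares 0 with 1 or more to "see if the subject has changed (gained or lost) or maintained, reflexes", is consistent with it but concerns reflexes only.

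**Conclusion.** The point holds in limited form. The plan's mapping turns an unchanged score lying between two expected values into a shift of one expected-value gap: 1, 2 or 3 points on the illustrative sets. The shift is a worsening if higher scores are better and a false improvement if an item runs the other way; it is spurious in either case. It reaches the baseline-to-worst table, and the baseline-to-best table only when the off-scale score persists at every assessment.

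The conclusion assumes that off-scale scores between expected values occur at both baseline and a later assessment. The SAP anticipates "scores outside the set of expected values" by writing a rule for them, but says nothing about how often they arise or whether they lie between expected values. On-scale records are unaffected. A reader might infer that the trial's efficacy conclusions are touched; they are not, since these are descriptive safety displays outside the ranked testing sequence in Section 5. Masking of an arm difference is possible in principle, but its size cannot be stated from the document.

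**What to change.** In Section 7.1.4, for the shift tables, either map off-scale scores in the same direction at baseline and post-baseline, or count no shift when the recorded scores are equal and take the direction of any change from the recorded scores. List every mapped record with its raw and mapped scores, so that falls within one step remain visible. State what happens to scores beyond either end of the scale. If a harm-leaning display is wanted, keep the present opposite-direction rule only as a labelled worst-case sensitivity table.

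The cost is a sentence or two in the SAP and one listing; no new data are needed. The downside is small: same-direction mapping can merge some small recorded changes, including falls, into one category, and the listing shows these.
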